- PIVC and administration set (extension tubing) securement
 - Sutureless securement device
 - Sterile tape strips around PIVC
 - Non-sterile tape around PIVC
 - Non-sterile tape over PIVC dressing
 - Non-sterile tape around administration set
 - IV administration set securement device
 - Splint/bandage/tubular net
 - Site dressing only
 - Other (specify)
- IV connectors:
 - Extension tubing
 - Stopcock/3-way tap
 - Needleless connector directly attached to catheter hub
 - Cap attached to the end of the catheter
 - IV tubing directly connected to catheter
 - Other (specify)
 - None
- PIVC dressing type:
 - Tape only (type of tape: paper, plastic, soft cloth, silk, other (specify))

- Gauze and tape dressing
- IV FIX
- Transparent film dressing
- Transparent film dressing and tape
- Bordered film dressing
- No dressing
- Other (specify)

- Signs and symptoms at the PIVC site: yes, no. If yes:
 - Pain/tenderness on palpation
 - Redness > 1 cm from insertion site
 - Swelling > 1 cm from insertion site
 - Purulence
 - Itch/rash under dressing
 - Blistering/skin tears under dressing
 - Dried blood
 - Palpable hard vein cord beyond IV tip
 - Streak/red line along vein
 - Induration/hardness of tissues > 1 cm
 - Other (specify)
- Presence of any of the following clinical complications: phlebitis (grade 1-4; mechanical, chemical, infective), hematoma, ecchymosis, skin injury, local infection.
- Presence of any of the following mechanical complications: catheter dislodgement, occlusion, extravasation, infiltration (grade 1-4), leaking at the insertion site.
- Presence of any of the following quality issues: unstable PVIC, blood reflux, uncontrolled IV infusion rate, site dressing partially detached, site dressing totally detached (site exposed to environment), medical tape added to dressing edges, unclean dressing, discomfort at site with or without palpation, uncovered tubing access port, lack of visibility at the PIVC site.

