6.1 Study endpoints

- 6.1.1 Primary endpoint
- Proportion of PIVCs sites with at least one clinical or mechanical complication.
- 6.1.2 Secondary endpoints
- Proportion of PIVC sites with at least one clinical and one mechanical complication.
- Proportion of PIVC sites with at least one clinical complication and with each specific clinical complication.
- Proportion of PIVC sites with at least one mechanical complication and with each specific mechanical complication.
- Proportion of PIVC sites with at least one related quality issue and with each specific quality issue.
- Frequency distribution for the PIVC Standards of Practice.

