6.2.3 Secondary endpoint analyses

- The prevalence of PIVC-related clinical and mechanical complications among the PIVC sites audited at the participating acute care hospitals in Brazil will be determined as follows:
 - Prevalence (%) = (Number of audited PIVC sites with at least one clinical and one mechanical complication ÷ Number of audited PIVC sites) x 100
- The prevalence of PIVC-related clinical complications among the PIVC sites audited at the participating acute care hospitals in Brazil will be determined as follows:
 - Prevalence (%) = (Number of audited PIVC sites with at least one clinical complication ÷ Number of audited PIVC sites) x 100
 - Prevalence (%) = (Number of audited PIVC sites with each specific clinical complication ÷ Number of audited PIVC sites) x 100
- The prevalence of PIVC-related mechanical complications among the PIVC sites audited at the participating acute care hospitals in Brazil will be determined as follows:
 - Prevalence (%) = (Number of audited PIVC sites with at least one mechanical complication ÷ Number of audited PIVC sites) x 100
 - Prevalence (%) = (Number of audited PIVC sites with each specific mechanical complication ÷ Number of audited PIVC sites) x 100
- The prevalence of PIVC-related quality issues among the PIVC sites audited at the participating acute care hospitals in Brazil will be determined as follows:
 - Prevalence (%) = (Number of audited PIVC sites with at least one quality issue ÷ Number of audited PIVC sites) x 100
 - Prevalence (%) = (Number of audited PIVC sites with each specific quality issue ÷ Number of audited PIVC sites) x 100

The definitions of clinical and mechanical complications, as well as of quality issues, are detailed in Section 3.3 and Appendix I.

PIVC Standards of Practice will be summarized using descriptive statistics.

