12.1 Appendix I– Definition of PIVC-related complications

Table A – Definition of clinical PIVC-related complications

Complication	Definition
Phlebitis	
Presence of pain, tenderness, warmth, erythema or streak formation at or near the PIV insertion site due to movement, chemical irritant and/or bacteria. Thus, according to etiology, phlebitis may be classified as:
 
 • Mechanical: If the catheter is dislodged or not secure (i.e., moves) • Chemical: If the patient is receiving, KCl, IV fluids or antibiotics that tend to cause phlebitis • Infective: if local infection is also present 
The degree of phlebitis is rated using a scale ranging from 1 to 4^a:
 
 • Grade 1: Erythema at access site with or without pain. • Grade 2: Pain at access site with erythema and/or edema. • Grade 3: Pain at access site with erythema, streak formation, and/or palpable venous cord. • Grade 4: Pain at access site with erythema, streak formation, palpable venous cord >1 inch in length, and/or purulent drainage.
Hematoma	A localized swelling that is filled with blood caused by a break in the wall of a blood vessel.
Ecchymosis	Similar to a hematoma. A subcutaneous spot of bleeding (from extravasation of blood) with diameter larger than 1 centimeter.
Skin injury	Superficial damage to the skin as seen by redness, tears, or erosion of the skin, or development of blisters in an area exposed to medical adhesive and lasting for 30 minutes or more.
Local infection	Redness and/or induration within 2 cm of exit site with or without purulent drainage.

a. From: Alexander M. Corrigan A. Infusion Nurses Society: Infusion nursing an evidence-based approach. St. Louis, Mo.: Saunders-Elsevier; 2010.

Table B – Definition of mechanical PIVC-related complications

Complication	Definition
Catheter dislodgement	Movement of the PIV catheter out of the insertion site to the point it cannot be safely used, excluding infiltration.
Occlusion	Stopping or slowing of I.V. fluid flowing from the I.V. bag into the bloodstream. Signs: one is unable to easily flush fluid into the catheter without resistance. Causes: blood clotting in the catheter, kinking of the catheter or tubing, an admixture of medications/fluids or a venous thrombosis.
Extravasation	Accidental infiltration of a vesicant or chemotherapeutic drug into the tissues surrounding the IV site resulting in edema and/or tissue necrosis.

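### Redness alone meets both local infection and grade 1 phlebitis, so the by-type prevalence of local infection is biased upward and the infective label does not discriminate among red sites

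*Combined protocol and SAP*

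**What the plan says.** Appendix I, Table A, holds all the relevant definitions.

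- Local infection: "Redness and/or induration within 2 cm of exit site with or without purulent drainage". Either sign is sufficient, pus is optional, and there is no cause or exclusion clause.
- Phlebitis, general entry: "Presence of pain, tenderness, warmth, erythema or streak formation at or near the PIV insertion site due to movement, chemical irritant and/or bacteria".
- Phlebitis, lowest grade: "Grade 1: Erythema at access site with or without pain".
- Phlebitis, etiology: "Infective: if local infection is also present".
- Skin injury (the entry goes on to name adhesive and a duration of at least 30 minutes): "Superficial damage to the skin as seen by redness, tears, or erosion of the skin, or development of blisters in an area exposed to medical".

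Section 3.4.1 also has the auditor tick signs at each site. One is "Redness > 1 cm from insertion site". Purulence is a separate item on the same list.

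The by-type results are a secondary objective (Section 2.2) and a secondary endpoint (Section 6.1.2): "Proportion of PIVC sites with at least one clinical complication and with each specific clinical complication". Section 6.2.3 computes each one as "Number of audited PIVC sites with each specific clinical complication" over all audited sites. No section ranks the diagnoses, excludes one when another is present, or provides for adjudication.

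**The concern.** The same sign meets more than one definition, and one of those definitions then sets the etiology of another. A red site with nothing else satisfies local infection and the grade 1 phlebitis sign. Because local infection is then present, the phlebitis is infective by rule.

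The plan itself recognises redness that is not infection. Section 5.2 lists mild to moderate redness at the adhesive among the anticipated skin reactions, Table A accepts adhesive redness as skin injury, and phlebitis may be mechanical or chemical. Any such redness within 2 cm of the exit site also meets local infection.

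The published by-type figure for local infection is at stake, together with the meaning of the infective sub-class. Section 6.2.1 also presents results by hospital and ward, and the auditors are employees of each site (Section 3.3). An auditor who follows the table and one who applies clinical judgement can code the same site differently. Sections 1.2 and 3.1 make these data the first phase of a pre-post study, and Section 1.2 says the second phase follows the introduction of a dressing. A change in adhesive redness alone could then look like a change in local infection.

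**Working it through.** **Figure to reproduce.** The plan states none on this point. The only number used from it is the planned minimum of 3 hospitals × 100 = 300 PIVCs (Sections 3.7 and 6.3).

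**Step 1: the definitions as rules.** Take access site, exit site and insertion site as the same place. Let R be redness there (within 2 cm) and I be induration within 2 cm.

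- Local infection = R or I.
- Grade 1 phlebitis sign = R.
- Infective phlebitis = phlebitis and local infection.

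R alone makes the first two true, and so the third whenever the site is called phlebitis. As a check, seven signs (redness, pain, edema, induration, streak, cord, purulence) give 2^7 = 128 presence/absence patterns. Redness is present in 2^6 = 64 of them, and all 64 meet both local infection and the grade 1 sign. Phlebitis avoids the infective label only with neither redness nor induration within 2 cm, for example grade 2 on pain plus edema alone.

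**Step 2: direction.** Let t be the proportion of sites with true local infection and r the proportion with non-infective redness within 2 cm. Assume every true infection shows redness or induration there, so that none is missed. Then

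counted prevalence = t + r, and counted ÷ true = 1 + r/t.

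The bias equals r and cannot be negative.

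**Step 3: size, by assumption only.** The documents give neither t nor r. With n = 300:

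| True t | True sites | Counted if r = 3% | Counted if r = 15% |
|---|---|---|---|
| 0.5% | 1.5 | 10.5 (3.5%), ratio 7 | 46.5 (15.5%), ratio 31 |
| 1% | 3 | 12 (4%), ratio 4 | 48 (16%), ratio 16 |
| 2% | 6 | 15 (5%), ratio 2.5 | 51 (17%), ratio 8.5 |

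The ratio runs from 2.5 to 31, which shows how little the documents fix it.

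**Step 4: composites.** The primary endpoint and the any-clinical-complication endpoint count a site once if at least one qualifying complication is present. A red site is positive under one label or under three, so double labelling adds nothing. If an auditor declines the phlebitis label, redness within 2 cm still counts as local infection and the site stays positive.

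**Step 5: checking codes against the sign list.** The redness item has a 1 cm threshold, local infection uses 2 cm, and the phlebitis entry has no size limit. Redness of 1 cm or less can meet both definitions with the sign left unticked. Purulence is recorded per site without a threshold, so local infection with and without pus can be tabulated from planned data. Section 6.2.3 does not plan to do so.

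**The case against.** Several objections carry weight.

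- **The phlebitis entry has a cause clause.** It requires the sign to be due to movement, an irritant or bacteria, so an auditor may decline to call a red site phlebitis. That stands, and not every red site need become infective phlebitis. Local infection has no such clause, so its over-count remains.
- **Auditors are experienced and trained.** Section 3.3 requires extensive PIVC experience and site-assessment training, runs a pilot center first and lets the monitor ask for retraining. This may limit disagreement, and the documents do not show that hospitals will in fact differ. Training on the table as written, however, teaches the overlap.
- **The etiologies are not exclusive.** A reader might infer that the infective class empties the mechanical and chemical classes. The documents do not support this: each class has its own trigger, the causes are joined by and/or, and a site may carry more than one. Only the infective label loses its power to discriminate.
- **The data can partly sort it out.** A reader might infer that nothing can be recovered afterwards. Purulence, pain, induration, streak and cord are all recorded, so a split by purulence is possible. What is missing is a plan to report it and a redness item that matches the definition.
- **Etiology is not a named endpoint.** Sections 6.1.2 and 6.2.3 name each specific clinical complication; etiology appears as a sub-classification of phlebitis in Sections 3.3 and 3.4.1. That stands. The main damage is therefore to local infection, which is a named type.

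**Conclusion.** The overlap follows directly from the wording of Table A. Followed as written, the type-specific prevalence of local infection is biased upward by whatever non-infective redness lies within 2 cm of the exit site, and the infective label does not discriminate among erythematous phlebitis sites. Adhesive redness that qualifies as skin injury can add to the same over-count.

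The direction rests on the definitions and on the plan's own recognition of non-infective redness. The size does not come from the documents. A reader might be tempted to quote a fixed multiple, but the table above depends wholly on assumed rates. Taking purulence as the true standard would not settle it either, because infection without pus would be missed.

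A reader might also infer that the primary result is inflated. Double labelling does not change it, nor the any-clinical-complication endpoint. This is a defect in secondary, by-type reporting that should be corrected before auditors are trained.

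**What to change.** 1. Keep the Table A signs as they stand for the composite endpoints. Redefining local infection to require pus could remove induration-only sites from the primary endpoint, since induration is not among the listed phlebitis signs.
2. In the by-type results of Section 6.2.3, report local infection separately with and without purulence, and give infective phlebitis the same split. Redness-only sites are then not presented as confirmed infection.
3. Have the study team state in Table A, before auditor training, how redness alone is allocated among phlebitis, local infection and skin injury. The clinical criterion is theirs to choose.
4. In the Section 3.4.1 sign list, replace the thresholded redness item with redness yes/no plus greatest extent in cm, so that the coded complication can be checked against the 2 cm definition.

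The cost is a wording change in Table A, one changed questionnaire item and extra table rows for the split. The with-purulence figure is conservative because it omits infection without pus, and the report should say so.

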 - All patients receiving IV medication, electrolyte or solution
 - ICU patients only
 - Limited to patients receiving specific medications
 - None of the patients
 - Other (specify)
 - Not defined
- Responsible person who adds medications and electrolytes to IV infusion bottles or bags:
 - Nurse
 - Pharmacist
 - Physician
 - Nurse technician
 - Other (specify)
 - Not defined
- Environment where medications and electrolytes are added to IV infusion bottles or bags:
 - Nurses' station
 - Medication room
 - Patient's room/ward
 - Pharmacy
 - Not defined
- Socio-demographic variables:
 - Date of birth
 - Initials
 - Gender

- Individual PIVC variables:
 - Date and time of PIVC audit
 - Date and time of PIVC insertion
 - Responsibility for PIVC insertion:
 - Nurse
 - Physician
 - Nurse technician
 - Other (specify)
 - Unknown/Not documented
 - Department where PIVC was inserted:
 - Emergency department
 - Operating room
 - Intensive or Critical Care Unit (ICU)
 - General ward/clinic
 - Radiology or other procedure room
 - Ambulance/Emergency Medical System (EMS)
 - Other hospital
 - Unknown/Not documented
 - PIVC location:
 - Left or right hand
 - Left or right wrist
 - Left or right forearm
 - Left or right antecubital fossa
 - Left or right upper arm
 - Left or right foot
 - Left or right side of the head
 - Other (specify)
 - Reason for PIVC insertion:
 - IV fluids
 - IV medications
 - Blood sampling
 - Patient unstable/requiring resuscitation
 - Blood product transfusion
 - Parenteral nutrition
 - Chemotherapy
 - Unknown/Not documented
 - Other (specify)
 - Assessment of PIVC site is documented in the patient chart in the last 24 hours: yes, no
 - Site labeled with date and time of catheter insertion: yes, no.
 - Site overdue for relocation: yes, no. If yes: description for absence of relocation in medical records (yes, no)
 - Use of PIVC: continuous, intermittent

- Flush solution used to keep the PIVC open:
 - No flushing
 - 0.9% sodium chloride
 - Heparin/heparinized saline solution
 - Other (specify)
 - Not applicable (PIVC used continuously)
 - Unknown/Not documented
- IV medications and solutions infused using this PIVC within the last 24 hours:
 - Fluids without electrolytes
 - Antimicrobials
 - Analgesics
 - Sedation
 - Other (specify)
 - None
 - Unknown/Not documented
- PIVC gauge/size:
 - 14G (orange)
 - 16G (grey)
 - 18G (green)
 - 20G (pink)
 - 22G (blue)
 - 24G (yellow)
 - 26G (purple)
 - Steel needle
 - Not visible
 - Other (specify)

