6.2.2 Primary endpoint analysis

The prevalence of PIVC-related complications among the PIVC sites audited at the participating acute care hospitals in Brazil will be determined as follows:

- Prevalence (%) = (Number of audited PIVC sites with at least one clinical or mechanical complication ÷ Number of audited PIVC sites) x 100

The definitions of clinical and mechanical complications are detailed in Section 3.3 and Appendix I.

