Infiltration	When a solution or medication enters the surrounding tissues due to catheter dislodgement or vein ruptures. Recognized by increasing edema at or near the venipuncture site. The degree of infiltration is rated using a scale ranging from 1 to 4: 
 Grade 1: Skin blanched; edema <1 inch in any direction; cool to touch; with or without pain. Grade 2: Skin blanched; edema 1-6 inches in any direction; cool to touch; with or without pain Grade 3: Skin blanched, translucent; gross edema>6 inches in any direction; cool to touch; mild-moderate pain; possible numbness. Grade 4: Skin blanched, translucent; skin tight, leaking; skin discolored, bruised, swollen; gross edema>6 inches in any direction; deep pitting tissue edema; circulatory impairment; moderate-severe pain; infiltration of any amount of blood product, irritant, or vesicant.
Leaking at the infusion site	IV fluid found under the dressing that is exiting the catheter insertion site.

a. From: Alexander M. Corrigan A. Infusion Nurses Society: Infusion nursing an evidence-based approach. St. Louis, Mo.: Saunders-Elsevier; 2010.

Table C – Definition of PIVC-related Quality issues

Issue	Definition
Unstable PIVC	Catheter moves when touched or when patient moves yet is still functioning.
Blood reflux	Blood observed in the tubing, not associated with a recent blood infusion.
Uncontrolled IV infusion rate	Infusion rate controlled by only a roller clamp or by gravity.
Site dressing partially detached	Dressing is lifted off skin, but insertion site not exposed to environment (25% or greater)
Site dressing totally detached	Dressing is lifted off skin and insertion site exposed to environment
Medical tape added to dressing edges	Tape added to the edges of the insertion site cover or dressing to prevent the dressing from lifting up off the skin either due to the presence of edge lift or to prevent lift from occurring.
Unclean dressing	Stains or dirt observed on the dressing due to blood, food, secretions and/or other outside contaminants
Discomfort at the site with or without palpation	When subject states that the catheter is painful or uncomfortable, if asked, OR when subject complains of pain when the catheter insertion site is touched (palpated).
Uncovered tubing access port	An access port that is open to the environment without a cover or cap

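### The plan does not say how occlusion is judged in a PIVC that is not infusing, yet divides by all audited PIVCs, so occlusion prevalence, and to a lesser degree the primary composite, may read low

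*Combined protocol and SAP*

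**What the plan says.** - **Definition.** Appendix I, Table B, defines occlusion as "Stopping or slowing of I.V. fluid flowing from the I.V. bag into the bloodstream" and gives as its sign that "one is unable to easily flush fluid into the catheter without resistance". The definition needs flow and the sign needs a flush.
- **Audit procedure.** Sections 3.3 and 3.4 name two sources of PIVC data: the medical record and observation of the site. Table 1 lists eligibility review, consent and questionnaire completion for the audit day. A flush or patency check is neither required nor excluded.
- **Which PIVCs count.** Section 3.4.1 records "Use of PIVC: continuous, intermittent" and lists a capped catheter end among the connector options, so idle PIVCs are in the sample.
- **Answer options.** For mechanical complications, Section 3.4.1 lists presence only. Other items in that section, such as flush solution and gauge, do offer answers for not applicable, unknown or not visible.
- **Denominators.** Section 6.2.3 uses "Number of audited PIVC sites with each specific mechanical complication ÷ Number of audited PIVC sites". Section 6.2.2 uses "Number of audited PIVC sites with at least one clinical or mechanical complication ÷ Number of audited PIVC sites", so occlusion also feeds the primary endpoint.
- **Missing data.** Sections 6.2.1 and 6.4 rule out imputation. Neither says what happens to an item that could not be assessed.

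**The concern.** If a catheter is idle and nobody tests it, neither the definition nor the sign of occlusion can be observed at the bedside. With no other answer available, the auditor will probably leave occlusion unmarked, and the formulas then treat the PIVC as a tested negative. Missed occlusions can only push the occlusion prevalence (a secondary endpoint) and the primary composite downwards.

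The result would also depend on how many PIVCs happen to be idle at audit. That matters in three places:

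- Section 6.2.1 presents results by hospital and ward, where the idle share may differ.
- Section 6.2.4 relates PIVC characteristics to complications. Intermittent use could look protective only because occlusion is harder to detect there.
- Sections 1.2 and 3.1 make these data the baseline of a pre-post comparison. A change in the idle share between audits could pass for an intervention effect.

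**Working it through.** **The plan's own figure.** Sections 3.7 and 6.3 give at least 100 PIVCs at each of three hospitals: 3 × 100 = 300, as stated. Section 6.3 says that no formal sample size calculation was made, so there is no planned precision or expected prevalence to reproduce.

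**Inputs.** Only n = 300 is in the documents. The rest are assumptions:

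- p = true occlusion prevalence, taken as equal in idle and infusing PIVCs: 2%, 5%, 10%
- c = share of PIVCs neither infusing nor flushed at audit: 20% to 80%
- s = share of occlusions in those PIVCs that are found from the chart: 0, 0.5, 1
- q = prevalence of any other clinical or mechanical complication, independent of occlusion: 35%

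**Formulas.**

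- Reported occlusion = p × [(1 − c) + s × c]
- Reported composite = 1 − (1 − q) × (1 − reported occlusion)
- Shortfall in the composite = (1 − q) × p × c × (1 − s)

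**Occlusion prevalence at p = 5%.**

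| c | s = 0 | s = 0.5 | s = 1 |
|---|---|---|---|
| 20% | 4.0% | 4.5% | 5.0% |
| 40% | 3.0% | 4.0% | 5.0% |
| 60% | 2.0% | 3.5% | 5.0% |
| 80% | 1.0% | 3.0% | 5.0% |

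Take c = 40% and s = 0. The assessable PIVCs number 300 × 0.60 = 180, and 180 × 0.05 = 9 cases are found. Over all PIVCs this is 9/300 = 3.0% (Wilson 95% CI 1.6 to 5.6). Over assessable PIVCs it is 9/180 = 5.0% (2.7 to 9.2).

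**Shortfall in the primary composite, in percentage points, at q = 35% and s = 0.**

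| p | c = 20% | c = 40% | c = 60% | c = 80% |
|---|---|---|---|---|
| 2% | 0.26 | 0.52 | 0.78 | 1.04 |
| 5% | 0.65 | 1.30 | 1.95 | 2.60 |
| 10% | 1.30 | 2.60 | 3.90 | 5.20 |

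For example, with p = 10% and c = 80%, the true composite is 1 − 0.65 × 0.90 = 41.5%. The reported composite is 1 − 0.65 × 0.98 = 36.3%, which is 5.2 points lower. At s = 0.5 every entry halves; at s = 1 every entry is zero. Over the same p and c, the range is 0.3 to 6.4 points for q = 20% and 0.2 to 4.0 points for q = 50%.

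**Scale.** At 35% prevalence and 300 PIVCs treated as independent, the 95% half-width is 1.96 × √(0.35 × 0.65 / 300) = 5.4 points. Unlike that sampling error, the shortfall does not shrink with more PIVCs.

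**Effect of a shift in the idle share.** At p = 5% and s = 0, moving c from 40% to 60% between two audits takes reported occlusion from 5% × 0.60 = 3.0% to 5% × 0.40 = 2.0%, with no true change.

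**The case against.** The other side has several good arguments.

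- **The loss is conditional.** The medical record is a data source, so a failed flush noted by ward staff can be recorded. Table B lists kinking among the causes, and a kink may be visible. The protocol does not forbid a patency check, and the content of the site-assessment training is not described. A reader might infer that every occlusion in an idle PIVC is missed; the documents do not support that. This stands, and it is why the bias is worded as possible and s runs from 0 to 1.
- **The problem does not extend to every item linked to an infusion.** A reader might infer that leaking and uncontrolled infusion rate are under-counted in the same way. Table C defines the latter as "Infusion rate controlled by only a roller clamp or by gravity". A capped catheter truly does not have that issue, so the all-PIVC proportion is a choice of denominator, and as a quality issue it never enters the primary composite. Leaking is recognised by fluid beneath the dressing, which can be seen with no infusion running. Both fall outside this point.
- **Some of the information is already collected.** Use type, flush solution, recent infusates and connectors are recorded, so occlusion could be stratified by use. This stands in part: continuous or intermittent use is only a proxy for the state of the line at audit and does not show whether patency was tested.
- **No test between hospitals or wards is planned.** True; Section 6.2.1 only presents results by hospital and ward. The planned pre-post use is the stronger reason to act.
- **Restricting the denominator changes the question.** Infusing and idle PIVCs may differ in true risk, so a rate among assessable PIVCs does not correct the all-PIVC rate. This stands and shapes the fix.

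**Conclusion.** The point holds for occlusion and, through it, to a lesser degree for the primary composite. The plan defines occlusion by flow or a flush, describes no patency check, includes idle PIVCs, lists no 'not assessable' answer and divides by all audited PIVCs. Untested idle PIVCs will therefore probably be counted as negatives.

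The direction is downward; the size is unknown. The composite shortfall of about 0.3 to 5.2 points assumes that no occlusion is found in idle PIVCs, that true risk is the same in idle and infusing PIVCs, and that other complications are independent at 35%. With true occlusion of 2 to 5% it is 0.3 to 2.6 points, well inside the 5.4-point half-width. The relative effect on the occlusion prevalence is larger: at s = 0 the reported figure is 80% down to 20% of the true one as the idle share rises from 20% to 80%.

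This does not invalidate the primary endpoint. It is a gap that costs little to close before the audit and cannot be closed from the planned data afterwards.

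**What to change.** **Individual PIVC Questionnaire (Section 3.4.1)**

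- Record whether an infusion was connected and intended to be flowing at audit. A stopped or slowed line counts as yes. Asking only whether an infusion is running would remove fully blocked lines from the denominator because of the outcome itself.
- Record occlusion as present, absent or not assessable, with the source of the finding (observation or record).

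**Section 6.2.3**

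- Report occlusion among assessable PIVCs beside the all-PIVC figure, with the number not assessable. Assessable means that an infusion was intended to be flowing, or that a flush or patency finding is documented in the record within a window fixed in advance.
- Show the result by source. If charts note only failed flushes, PIVCs that qualify through the record would push the assessable-only figure up.

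**Section 6.2.2**

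- Keep the all-PIVC primary figure. Add one sensitivity analysis for non-assessable occlusion: either the composite without occlusion, or a range running from no occlusion in non-assessable PIVCs to the assessable-group rate applied to them.

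**Post-intervention audit**

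- Apply the same items and rules.

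**Cost.** A few form items, one extra analysis, and a wider interval for the assessable-only figure (in the example above, 2.7 to 9.2% instead of 1.6 to 5.6%). That figure describes a different subgroup, so it supplements the all-PIVC figure and does not replace it. No patient procedure is added.
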